15.0 Compensation for Research-Related Injury

15.1 Compensation for Research-Related Injury: N/A

15.2 Contract Language: N/A

16.0 Consent Process

16.1 Consent Process (when consent will be obtained): Once subjects are removed from sedation and able to follow 3/3 one-step commands.

- Consent will occur in the hospital room of the subject. There will be no waiting period between initial consent and initiation of study.
- Ongoing verbal consent to activity will be addressed daily, when the therapist approaches a subject for scheduled therapy.
- Consent will be obtained via pre-approved form.

16.2 Non English-Speaking Participants: Any non-English speaking individual who is being treated by a physical therapist and who is undergoing ECMO treatment would be eligible for consent. As advised by IRB, a line on the consent form indicating who facilitated consent in the case of a non-English speaker, has been added.

PROTOCOL TITLE: The Impact of Lower Extremity Weight-Bearing Leg Exercise During the Pre-Ambulation Phase of Individuals Undergoing Extracorporeal Membrane Oxygenation (ECMO)
VERSION DATE: 11/28/16

16.3 Participants Who Are Not Yet Adults (infants, children, teenagers under 18 years of age): N/A

16.4 Cognitively Impaired Adults, or adults with fluctuating or diminished capacity to consent: N/A

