- ECMO delivery is veno-venous with internal jugular catheter.

Exclusion Criteria

- Femoral catheter of any kind present.
- Veno-arterial ECMO setup.
- Sedation such that self-consent is not attainable.
- Medical instability, as determined by primary critical care physician.

Overview of Protocol for Aims 1-3:

Participants in either Group A (closed chain leg exercise group) or B (open chain exercise group) will progress through the established ECMO protocol led by their physical therapist. Participating therapists have extensive experience in working with patients on the Moveo who are in the ICU. Subjects will be assisted in the supine position from their bed to the Moveo device via a lateral transfer across a slide board to facilitate ease of movement.

Those in Group A will participate in leg exercise on the Moveo during item 4d of the ECMO protocol, whereby those in Group B will complete standard exercise as listed in item 4d. Group A participants will use the Moveo until subjective report of leg fatigue. Participants will self-select the pace of their leg exercise and the primary therapist will determine guidelines for percent of body weight lifted in accordance with standard practice physical therapy. Subjects will complete 1-4 sets of up to 25 reps of the squat exercise with 2 minutes of rest between each set. Subjects will receive physical therapy 5 days/week regardless of randomization into Group A or Group B.

Data Collection for Aims 1-3: Data will be collected on Day 0 (physical therapy evaluation day), Day 5, Day 10, Day 15, Day 20, Day 30, Day 45 (if applicable), and Day of discharge. Data collected will be categorized as specific to Aim 1 (time from initial physical therapy evaluation to initial ambulation), Aim 2 (functional outcomes) and Aim 3 (hospital outcomes). Recording of physiological data including heart rate (HR), blood pressure (BP), oxygen saturation (O2), and respiratory rate (RR) will be completed by trained physical therapists involved in the protocol at the onset of, and 1-minute post-conclusion of each therapy session. Therapy sessions are to be delivered at a frequency of five sessions per week.

- Functional Outcomes

- Leg strength as assessed by primary therapist via manual muscle test, using the Medical Research Council Sum Score (MRC Score)
- Grip strength, as assessed by hand dynamometer, completed by primary therapist

- 30-second sit to stand, completed by primary therapist

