Data and Safety Monitoring Plan

Study personnel who have completed HIPAA, CITI, and other data management training through the University of Minnesota Medical Center, Fairview and the University of Minnesota will be responsible for the collection, management, and analysis of study data.

Participants will be randomized to groups through a randomization service prior to study initiation. All participants will be assigned a subject number that will be stored on a computer at the University of Minnesota, which is password protected. Data collected from participant's medical records will be managed exclusively by the primary therapist and the PI, and stored in a password protected data management system through Research Electronic Data Capture (REDCap), available at the University of Minnesota.

In accordance with regulations, participant records will be stored for a minimum of three years following completion of the study. After the stated timeframe and if data is no longer needed, records will be destroyed.

Confidentiality

For the duration of the study and data analysis, precautions will be taken to ensure the confidentiality of protected health information (PHI). Such precautions include: the use of password-protected computer for data analysis, PHI storage in the REDCap management program, de-identification of forms and use of assigned subject number, and data collection completed by the primary investigator.

Potential Risks

Lower Extremity Exercise: As with any new exercise program, muscle fatigue or mild soreness may occur in the 24-48 hours following exercise. This minor effect will not impact mobility or function in any way.

Mobilization Protocol: Subjects participating are undergoing ECMO due to respiratory failure and are critically ill. To maximize safety and minimize risks, the primary physical therapist will communicate with the medical team daily to ensure subjects are appropriate for mobilization and participation in physical therapy. [name], Acute Care Surgery physician at the University of Minnesota Medical Center, Fairview, is the primary medical contact for these subjects and is actively involved in the implementation of the ECMO Mobilization Program. [name] is responsible for removing active physical therapy orders, as is any critical care physician, if an individual undergoing ECMO is no longer stable for mobilization or exercise. Orders will be verified daily, prior to physical therapy, by the primary therapist.

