Adverse Event Reporting

Subjects in this study are patients at the University of Minnesota Medical Center, Fairview. As a result, adverse events will be reported not only in the medical record of the subject, but also recorded by the investigator.

Any adverse event will be followed and assessed until it has been determined that the study treatment or participation is not the cause.

Adverse Events

Adverse events observed or reported will be recorded in the case histories of each participant to determine if:

1. The event is directly related to the study and should be classified as a serious adverse event (SAE)
2. A causal relationship exists between the adverse event effect and the investigational exercise/mobility program

Any adverse event not determined to qualify, as a SAE will be reported to the IRB with the continuing review progress report.

Stopping Rules

If a SAE occurs, which is deemed by the overseeing physician, [name], to be a direct result from the study intervention, the study will be put on hold and reviewed by the PI to determine whether or not the study can continue.

Any deviation from the intended investigational plan to protect the life or well being of a participant in an emergency will be reported to the IRB within 5 working days after the emergency occurred.

As a part of the consent process, participants will be notified that they can withdrawal at any time during the study. Data collected prior to withdrawal of any subject may still be used for data analysis. There is no compensation associated with this pilot investigation.

References

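### Delayed soreness, the one specific harm named for the leg exercise, is declared without effect, never asked about, and has no planned by-group summary

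*Combined protocol and SAP*

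**What the plan says.** Under Potential Risks, the Project Proposal says of the leg exercise that "muscle fatigue or mild soreness may occur in the 24-48 hours following exercise", and then: "This minor effect will not impact mobility or function in any way". No source or data are given for the second statement.

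Data Collection for Aims 1-3 schedules heart rate, blood pressure, oxygen saturation and respiratory rate "at the onset of, and 1-minute post-conclusion of each therapy session". The functional outcomes are leg strength, grip strength, the 30-second sit to stand, RASS and FSS-ICU. Neither that list nor the hospital outcome list has an item on soreness, pain or delayed fatigue.

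Under Adverse Events: "Adverse events observed or reported will be recorded in the case histories of each participant to determine if" the event is study-related and serious, and whether it was caused by the exercise programme. Non-serious events go to the IRB at continuing review. Statistical Considerations compares physiological, functional and hospital outcomes between groups and does not mention adverse events. Background & Significance includes safety and feasibility among the things the study is to determine.

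The therapist is in regular contact with each participant. Section 16.1 states: "Ongoing verbal consent to activity will be addressed daily, when the therapist approaches a subject for scheduled therapy". Data Collection adds: "Therapy sessions are to be delivered at a frequency of five sessions per week".

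**The concern.** The plan predicts one specific harm of the exercise, asserts that it is without consequence, and then collects nothing designed to test that assertion. Mobility and function are what Aims 1 and 2 measure, so whether soreness affects them is an open question in this trial.

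Exposure differs by arm: "Group A participants will use the Moveo until subjective report of leg fatigue", while Group B does the standard exercise. The primary therapist treats the participants and also performs the strength, grip and sit-to-stand tests, so knows the allocation. Events that are recorded only when someone notices or mentions them may be picked up to different degrees in the two groups.

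Two things are at stake. A trial that names safety as a purpose would have no planned statement, by group, about the harm it expected. And if Group A scored worse on leg strength or sit to stand on a collection day soon after exercise, nothing in the data would show whether soreness was part of the reason.

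**Working it through.** **The plan's own figures.** The documents give no soreness rate, error rate, power or effect size, so there is no calculation on this point to reproduce. The only sample-size figure is 2 x 12 = 24 recruited, aiming for 10 per group.

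**Step 1. Could the scheduled readings detect soreness?** They are four vital signs. None measures soreness, whether taken one minute or one day after exercise. Extending them in time would not help.

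**Step 2. Is there contact in the predicted window?** Inputs: five sessions per week (Data Collection for Aims 1-3) and a window of 24 to 48 hours (Potential Risks). In a repeating 7-day week the five gaps between sessions sum to 7 days and each is at least 1 day, so 7 - 5 = 2 extra days are shared out. There are C(7,5) = 21 ways to place five sessions:

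| Rest days | Placements | Gaps (days) | Next session within 1-2 days |
|---|---|---|---|
| Adjacent | 7 | 1, 1, 1, 1, 3 | 4 of 5 (80%) |
| Separate | 14 | 1, 1, 1, 2, 2 | 5 of 5 (100%) |

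This assumes sessions at similar times of day and continuing treatment. A Monday-to-Friday week (an assumption; the documents do not name the days) is the first row, with about 72 hours after the Friday session. Contact therefore usually falls inside the window, but no question is planned at it.

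**Step 3. What route is left?** Adverse events that are observed or reported. The route has no cut-off after a session, so soreness can be recorded, but it is unsolicited. Its stated uses are judging seriousness and cause and informing the IRB, not summarising by group.

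**Step 4. What could a solicited item show at this size?**

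If 0 of n participants report soreness, the one-sided 95% upper limit is 1 - 0.05^(1/n):
- n = 10: 1 - 0.05^(1/10) = 25.9%
- n = 12: 1 - 0.05^(1/12) = 22.1%

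Power of a two-sided 5% Fisher exact test, by summing over all pairs of binomial outcomes. The rates are assumed; none is in the documents.

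| Assumed rates | 10 per group | 12 per group |
|---|---|---|
| 20% vs 40% | 6% | 9% |
| 20% vs 60% | 25% | 39% |
| 20% vs 80% | 64% | 81% |

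Only a very large difference would be detected with any reliability. The output should be descriptive, without a test.

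**The case against.** The strongest case against the point has four parts.

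- **Recording exists.** Adverse events go into the medical record and are also recorded by the investigator, are followed until participation is ruled out as the cause, and, if non-serious, reach the IRB. The therapist also checks with the medical team and verifies orders daily. This stands: a reader might infer that the predicted harm would go wholly unrecorded, and the documents do not support that.
- **The check timing is not the fault.** A reader might infer that soreness is missed because safety checks stop one minute after exercise. That fails twice: vital signs would not show soreness at any time, and readings are also taken at the onset of the next session, usually within 24 to 48 hours.
- **The sentence changes no analysis.** A reader might infer that it prejudges Aims 1 and 2. It is a risk statement. Time to ambulation and function are still measured and compared, so any net effect of soreness counts in those results. What is lost is the ability to attribute a difference to soreness.
- **Unreliable reporting is not shown.** Participants must follow 3 of 3 one-step commands and be able to consent for themselves, and Group A's exercise already ends on the participant's own report. Unequal noticing by unblinded therapists is possible, but the documents give no rates from which to size it.

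It can also be said that soliciting a mild symptom in a small pilot has little decision value. For inference that is right. It does not answer the absence of any by-group safety summary in a study that names safety as a purpose.

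**Conclusion.** The point holds as a minor one. In the supplied text, delayed fatigue or soreness is the only specific harm named for the leg exercise. Its lack of effect is asserted without support, it is captured only if someone volunteers or notices it, and neither it nor adverse events generally have a planned summary by group. The defect is the missing question and the missing table.

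Its size is limited. It biases no planned analysis, and at 10 to 12 per group no soreness in a group would still be compatible with a true rate of up to about 22% to 26% (one-sided 95%). It is worth correcting because the information cannot be recovered after the trial and the contact needed to collect it already takes place.

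The conclusion rests on the supplied text. Section 11.0 of the local form refers risks to section 14.0 of a main protocol, and the Project Proposal supplied has no section with that number. The timing result assumes sessions at similar times of day and treatment that continues.

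**What to change.** 1. In Potential Risks, delete the sentence "This minor effect will not impact mobility or function in any way".
2. At the daily verbal-consent contact in section 16.1, have the therapist ask every participant in both groups the same two yes/no questions: any leg soreness since the last session, and if so, does it limit today's session. Allow non-verbal answers. Because the recall period runs from the last session, it also covers the longer gap over rest days. Do not ask about fatigue: Group A exercises to leg fatigue by design, so the item would differ between arms by construction. Delayed fatigue then remains with the adverse event route.
3. In Statistical Considerations, add a descriptive table by group, regardless of attribution, of all adverse events, participants with any soreness, and participants with any soreness-limited session. Give exact 95% confidence intervals for participant proportions only. Report session totals as plain counts, because sessions repeat within a participant and are not independent. Plan no hypothesis test.

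The cost is a few seconds per session, the matching REDCap fields and one table. No visit is added, and the answers are recorded only, with no change to treatment. The limitation that remains is that the person asking knows the allocation; identical wording and timing in both arms reduce the problem without removing it.
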